Identification and treatment of gait abnormalities in children and adolescents with Dravet syndrome

Research Protocol for posting on ClinicalTrials.gov PRS

Protocol Registration number: NCT03857451

Date: 07 February 2017

1. Background

The gait pattern in children and adolescents with DS was first described as "crouch gait" by Rodda et al., using 2D video analysis, clinical examination and X-ray of the lower limbs [1]. Later, Rilstone et al confirmed this "crouch" pattern in adults [2]. In addition to the gait deviations described, the children with DS also showed an enlarged internal hip rotation and a decreased passive knee and hip extension and an increased external tibial torsion and pes plano valgus observed with increasing age [1]. Based on these observations, Rodda hypothesised that a combination of malalignment and muscle weakness of the lower limbs lies at the root of the observed gait disorders [1]. However, this hypothesis can only be confirmed by 3D gait analysis in combination with measurements of muscle strength, which has not yet been carried out.

From the study of Rodda et al. "crouch gait" appears to develop in children with DS between 6 and 12 years [1], followed by a progressive decline in the gait pattern with increasing age [1, 2]. As mentioned, the passive movement limitations and the bony deformities aggravate by increasing age [1]. It is known that "crouch gait" in other patient populations usually arises in early adolescence [3]. This period is characterized by a growth spurt, in which body length and weight increase faster than muscle strength, reflecting the "crouch" pattern [3]. "Crouch gait" is known as a very complex, progressive disorder, profound understanding of the various causal factors is required to adequately treat this pattern. In order to gain full insight into the causes of the abnormal gait pattern, a longitudinal follow-up of patients is therefore necessary to monitor the influence of various factors, such as growth, a possible decrease in muscle force, but also the characteristic psychomotor retardation.

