No literature is known on the treatment of gait disorders in patients with DS. Researchers do mention the use of corrective insoles [4], orthopaedic shoes and ankle-foot orthosis [1], mainly based on clinical expertise and results of scientific research in other populations. Orthopaedic procedures are also applied to correct bone-like abnormalities with the aim of optimizing the gait pattern [1]. The effectiveness of these interventions in patients with DS is unknown. To increase the quality of life of the individual patient, it is essential to keep patients with DS active and mobile for as long as possible. Interventions can focus on improving the strength and/or correction of the biomechanics of the gait pattern. It is extremely important to also think about prevention and determine at what age one can already intervene to correct small deviations in biomechanics (e.g. by splints) to prevent children from entering a vicious circle of serious gait disorders, such as "crouch". When drawing up a treatment plan, it is possible to rely on the expertise of the treatment of gait abnormalities in other neuromotor disorders (cerebral palsy, spina bifida), but it is essential to adapt the proposed treatment plan to the specific characteristics of patients with Dravet syndrome.

2. Purpose of the research

The ultimate objective of this project is to draw up adequate, scientifically based, treatment for reduction and, if possible, prevention of gait disorders in children with DS.

3. Method

The research consists of 2 parts: a retrospective part and a prospective part. In the retrospective part, children's developmental status and potential developmental delay is described based on file data. In the prospective part, the children with DS are contacted and their gait pattern is evaluated.

Patient Recruitment:

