Passive changes mean muscle contractures and bone-like abnormalities. Previous research identified both flexion and extension defects, as well as malrotations in children with DS [1]. Prevention of muscle contractures can be done by stretching during physiotherapy as well as by using night equipment for positioning. Active changes mean that we have a loss of strength that was suggested in children with DS [1]. Here too, after sufficient insights into the natural course, preventive, but also corrective action can be done using physiotherapy. Finally, there are also possibilities to directly affect the gait pattern, for example, by using orthotics that can restore biomechanical functions.

Use of orthotics as well as frequency of physiotherapeutic interventions will be listed. On the basis of the results of the 3D gait analysis and the longitudinal follow-up of patients, a decision will be taken on the usefulness and application of any interventions in consultation with the treating neurologist and physiotherapist.

Statistical analysis plan

The statistical analysis will mainly include descriptive statistics. Gait parameters will be compared between DS and healthy controls using a t-test or a non-parametric alternative. Changes in gait pattern, detected by annual retesting, will be evaluated using a mixed models design.

4. Relevance of the research

Knowledge and insights from this project will directly improve quality of life in patients with Dravet syndrome by optimizing the treatment of gait abnormalities, allowing the individual to remain mobile for longer and thus contribute to increased independence and self-reliance of the individual. This sets the research within the strategic cluster 'Health & Well-being' with a focus on prevention and treatment of gait problems in brain disorders based on personalized therapy. A personalised treatment plan can only be achieved if a thorough identification of the gait defects and its causes have been carried out, which can only be done on the basis of 3D gait analysis. Moreover, prevention can only be done and intervened early, when the data of a longitudinal follow-up of the gait pattern are available in children with DS.

5. References

- 1.Rodda, J.M., et al., *Progressive gait deterioration in adolescents with Dravet syndrome*. Arch Neurol, 2012. **69**(7): p. 873-8.

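### If interventions guided by the study's gait results start during follow-up, must the protocol say whether its mixed model shows the natural course or the course under care?

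*Protocol*

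**What the plan says.** In section 3 (Method), under Interventions, the protocol states: "On the basis of the results of the 3D gait analysis and the longitudinal follow-up of patients, a decision will be taken". The decision covers both the usefulness and the application of interventions and is made "in consultation with the treating neurologist and physiotherapist". On the recording of care it says: "Use of orthotics as well as frequency of physiotherapeutic interventions will be listed". Under Statistical analysis plan, the only longitudinal sentence is: "Changes in gait pattern, detected by annual retesting, will be evaluated using a mixed models design". It names no outcome, time scale, covariate or role for treatment.

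Four other statements bear on what the follow-up is for:
- Section 1, Background: "a longitudinal follow-up of patients is therefore necessary to monitor the influence of various factors". The examples given are growth, muscle force and psychomotor retardation.
- Section 1, on orthoses and orthopaedic procedures already in use: "The effectiveness of these interventions in patients with DS is unknown".
- Section 3, Interventions, on loss of strength: "after sufficient insights into the natural course, preventive, but also corrective action can be done using physiotherapy".
- Section 4, Relevance of the research: "prevention can only be done and intervened early, when the data of a longitudinal follow-up of the gait pattern are available".

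**The concern.** The same gait results appear to serve two purposes. They inform decisions about interventions, and they are the outcome from which change over time is estimated. If a child starts a new intervention after one annual test and it helps, later tests reflect it. The average change is then the course under results-guided care. A reader who took it for the natural course would judge deterioration to be slower than it is without new interventions, and that judgement is meant to inform when prevention should begin.

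The protocol does not say that interventions wait until the last retest, nor whether later tests are kept, separated or modelled. Orthotics and physiotherapy are recorded, but the analysis text gives them no role. Orthopaedic procedures are not among the items to be recorded.

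**Working it through.** **1. What the text says about timing.** The decision rests on the gait analysis *and* the longitudinal follow-up. Physiotherapy to prevent or correct loss of strength comes after insight into the natural course. Early prevention becomes possible once the longitudinal data exist. Section 2 gives the aim as drawing up a treatment. All four fit a sequence of observing first and acting later. None is an explicit rule, and deciding with treating clinicians leaves earlier action open. The text is ambiguous, not contradictory.

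**2. What the analysis claims.** The analysis sentence speaks of changes in gait pattern. It does not call the result the natural course; that term occurs once, in the sentence on physiotherapy for loss of strength. A mixed model can carry treatment covariates, and the wording excludes none.

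**3. Possible size.** The protocol has no figure to reproduce: it gives no slope, SD, number of retests or intervention effect. Its one relevant number is the target of about 50 participants (30 + 20). The rest is assumed: 4 annual tests, true worsening 2.0 degrees/year, first-test mean 15 (SD 8), slope SD 1, visit SD 4, and an intervention that lowers all later tests by a fixed step.

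One case can be done by hand. Let 15% of untreated children start each year, regardless of severity. The shares treated at tests 0 to 3 are 0, 0.15, 1 − 0.85² = 0.2775 and 1 − 0.85³ = 0.3859. The centred times are −1.5, −0.5, 0.5 and 1.5, with sum of squares 5. With complete data, each degree of benefit lowers the mean slope by

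(−0.5 × 0.15 + 0.5 × 0.2775 + 1.5 × 0.3859) / 5 = 0.6426 / 5 = 0.1285.

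- No effect: 2.00.
- 3 degrees: 2.00 − 3 × 0.1285 = 1.61.
- 6 degrees: 2.00 − 6 × 0.1285 = 1.23.

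Simulation (400 data sets per scenario, random intercept and slope) gives the same values here. When the start follows a measured value above 20, the slopes are 2.00 / 1.47 / 0.95; above 25, they are 2.00 / 1.68 / 1.37.

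If the intervention instead removes a fraction r of the yearly worsening during a share f of person-time, the slope is 1 − f·r times the natural one: 0.94 for f = r = 0.25, 0.75 for f = r = 0.5, and 0.25 for f = 0.75 with r = 1.

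**4. Whether extra models would help.** Two candidates are (a) a time-varying intervention term and (b) using only tests up to the first new intervention. When decisions depend on measured gait or chance and the effect is an immediate step, (a) gives 2.00 to 2.03 and (b) 2.01 to 2.03. Each can fail:
- If the intervention slows worsening instead of producing a step, (a) gives about 1.8 to 1.9 with 50% slowing and 1.6 to 1.8 with 100% slowing, even when decisions rest only on measured gait or chance.
- If clinicians act on information outside the model, the results are as follows (true slope 2.00; Monte Carlo standard error 0.013 to 0.026):

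| What clinicians know | Unadjusted, 0 / 3 / 6 degrees | (a) | (b) |
|---|---|---|---|
| Next year's true value >20 | 2.00 / 1.48 / 0.95 | 1.52 | 1.22 |
| Next year's true value >25 | 2.00 / 1.68 / 1.37 | 1.67 | 1.60 |
| Progression >2.5/year, noisy and delayed | 2.00 / 1.66 / 1.33 | 1.78 | 1.63 |
| Progression >2.5/year, exact and immediate | 2.00 / 1.72 / 1.45 | 1.78 | 1.50 |

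With no effect, both models are worse than the unadjusted slope. With 3 degrees, (b) is further from 2.00 in all four rows (the third is close to simulation error), and (a) ranges from about equal to somewhat better. With 6 degrees, both are closer. Which analysis is best depends on an effect the protocol calls unknown. Model (b) also keeps only 66% to 83% of tests, with a standard error of 0.34 to 0.41 against 0.29 to 0.33.

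**The case for a change.** The strongest case for a change is that this is partly a design and data matter. What the follow-up is meant to show, and when decisions fall relative to retests, belongs in a protocol. Start dates and orthopaedic procedures that are not recorded at the time may be hard to recover, and a few sentences would cost little. Barefoot testing (Data Collection Procedures) limits the direct effect of worn orthoses but not lasting effects of physiotherapy, positioning or surgery.

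Part of this stands. Overlap is not excluded, the direction of the shift under an effective intervention is clear, and it needs no selection of the worst cases. Recording start dates and procedures would be good practice.

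It does not amount to a fault in the plan. The complaint is that the text is silent, and what it is silent on (the exact target of estimation, visits after an intervention, treatment covariates, sensitivity analyses) is ordinary SAP content. A separate SAP may exist and was not available. Use of orthotics and frequency of physiotherapy are already to be recorded, so an analyst can report or model them. The proposed addition would leave the main analysis and its estimate unchanged. It would add a label and two models that cannot be shown to do better.

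**Conclusion.** No change to the plan follows. The protocol leaves open whether interventions guided by its results overlap the annual retests, but its own wording leans towards action afterwards and its analysis sentence claims no more than change in gait. If overlap occurs and interventions work, the estimate is the course under the care given, and the report should call it that. An analyst with the recorded care data can see this and say so.

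The difference is zero if interventions have no effect or start after the last retest. In the scenarios with a step effect it is about 0.3 to 0.5 degrees per year for a 3-degree benefit (2.00 − 1.72 to 2.00 − 1.47) and 0.55 to 1.05 for a 6-degree benefit (2.00 − 1.45 to 2.00 − 0.95). Apart from the 50 participants, every input behind these figures is assumed. They show that the distinction can matter, not that it does here. This is a gap that sensible analysis and reporting fill, and no better method has been shown.

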Dravet syndrome has a prevalence of 1/15,000 to 1/30,000. In Flanders, an estimated 380 people would have been diagnosed with Dravet syndrome. In 2016, 70 patients were medically and paramedically monitored at the University Hospital Antwerp (UZA), at the Child Neurology Department. As this is a rather small patient population, attempts are made to reach all patients within the age range of 3 – 25 years with Dravet syndrome in the geographical area of Flanders and the south of the Netherlands. Approximately 50 participants are being sought, 30 of which are from UZA and 20 from other centres. Children can participate in the study if they are (1) diagnosed with Dravet syndrome, based on the criteria defined by Ceulemans and Cras in 2004 [5] and (2) are 3 years or older, have at least one year of walking experience and are up to 25 years at first inclusion. Exclusion criteria for participation are the prevention of a heavy epileptic seizure (status epilepticus or tonic-clonic seizure for more than 3 minutes) in the 24 hours prior to the study and/or insufficient cooperative for the removal of a 3D gang analysis.

A study officer from the UZA will invite patients who arrive at the Dravet consultation at the Child Neurology Service to participate in the study. In addition, a written call is launched via the newsletter of the parent association Stichting Dravet Syndrome Nederland/Vlaanderen. Interested parties can contact the aforementioned research officer who will provide further information.

Written consent is requested to the parent(s) or legal guardian of the children. The parents and the child are informed prior about the course of the study, expectations and risks.

A control population in accordance with the size and characteristics of the pilot group, of children and (young) adults with typical development or cerebral palsy will be composed of available data from previous research. UZ Leuven makes a database available to this end of gait analyses carried out for research at the KU Leuven [6]. In addition, a second control group will be composed of children and young adults who also have motor and developmental problems, whether or not in combination with epilepsy, due to a genetic condition that is not a mutation in the SCN1A gene.

Research Setting

All studies carried out for this study will take place in the M²OCEAN lab, UZA.

Data Collection Procedures

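### The test of DS against healthy controls contains no age, although participants are 3 to 25 years old and the protocol expects gait in DS to worsen with age

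*Protocol*

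**What the plan says.** Under Statistical analysis plan (section 3, Method), after stating that the analysis is mainly descriptive, the protocol names the cross-sectional test: "Gait parameters will be compared between DS and healthy controls using a t-test or a non-parametric alternative". A mixed model is reserved for changes seen on annual retesting.

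The other relevant statements are:

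- **Who enters** (Patient Recruitment): those who "are 3 years or older, have at least one year of walking experience and are up to 25 years at first inclusion". On numbers, "Approximately 50 participants are being sought".
- **Who the controls are** (Patient Recruitment): "A control population in accordance with the size and characteristics of the pilot group", which "will be composed of available data from previous research". Age is not named as one of the characteristics, and no matching method is given.
- **What is expected of age** (Background): crouch gait "appears to develop in children with DS between 6 and 12 years", "followed by a progressive decline in the gait pattern with increasing age".
- **Why age matters to the project** (Background): one needs to "determine at what age one can already intervene to correct small deviations in biomechanics".
- **Age-specific reference data** (Data analysis): these are mentioned as a way to identify abnormal gait, but are not linked to the test.

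**The concern.** The Background implies that the gap between DS and typical gait changes with age. The named test reduces that gap to a single mean difference (or its rank equivalent) over a 22-year age span. Two things follow even if the groups have the same ages.

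First, in an unpaired test all variation due to age is counted as noise. Intervals are then wider than they need be, in a rare disease where about 50 patients are sought.

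Second, the pooled difference depends on the ages that happen to enrol, because it averages children below the age at which crouch gait is said to appear with adolescents who have already declined. It cannot show at what age a difference emerges.

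A third problem is conditional: if the archive controls differ from the DS group in mean age, the comparison is also biased.

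**Working it through.** The protocol gives no significance level, power, effect size or SD, so there is no planned figure to reproduce beyond the recruitment split, 30 + 20 = 50. Everything below is illustration.

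**Inputs from the protocol:** about 50 DS participants, controls of similar number, ages 3 to 25.

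**Assumptions not in the protocol:** two-sided 5% level, ages uniform over the range, a straight-line age effect, and a true difference of 0.5 residual SD at the middle of the range.

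**1. Precision, same age slope in both groups, equal mean ages.** If age explains a share R² of the variance, the unpaired t-test sees a standardised difference of 0.5 × √(1 − R²) on 98 df. With age in the model it stays at 0.5. Power is from the noncentral t; the last two columns are simulated.

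| R² | Difference seen by t-test | t-test power | Power with age and group-by-age | t-test interval wider by |
|---|---|---|---|---|
| 10% | 0.474 | 65% | about 69% | 4% |
| 20% | 0.447 | 60% | about 69% | 11% |
| 40% | 0.387 | 48% | about 69% | 28% |
| 60% | 0.316 | 35% | about 69% | 57% |

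**2. Precision, age slope in DS only.** This is closer to the Background. With age explaining 10/20/40/60% of variance within DS, simulated t-test power is 67/64/58/46%, against about 69% with group-by-age. The t-test intervals are 2/5/14/31% wider. At 10% the loss is negligible.

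**3. Dependence on the age mix.** Suppose the DS effect is zero up to age 6, rises linearly to its full size at 12, and then stays constant.

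- Ages uniform on 3–25: the pooled difference is (3 × 0 + 6 × 0.5 + 13 × 1)/22 = 73% of the full effect.
- Ages uniform on 3–12: it is (3 × 0 + 6 × 0.5)/9 = 33%.

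Perfect age matching does not change this.

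**4. Bias, only if mean ages differ.** The SD of age on 3–25 is 22/√12 = 6.35 years, so a gap of g years shifts the difference by √R² × g/6.35 SD. For R² = 20% and g = 2 that is 0.447 × 2/6.35 = 0.14 SD. With no true DS effect, the nominal 5% test rejects in 6.4% of trials (1 year) or 10.7% (2 years) at R² = 20%, and in 7.8% or 16.7% at R² = 40%. With equal mean ages there is no such inflation. The protocol gives no gap.

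**5. Where to place the adjusted contrast.** Fixing it at age 14, the midpoint of 3–25, is safe only if the sample is centred there. With no age effect, the interval grows by about √(1 + (distance from the mean age)²/(age variance)).

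- Ages 3–18: mean 10.5, variance 15²/12 = 18.75, so √(1 + 3.5²/18.75) = 1.29.
- Ages 3–16: mean 9.5, variance 13²/12 = 14.08, so √(1 + 4.5²/14.08) = 1.56.

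Simulated power is about 48% and 35% respectively, against about 70% for the t-test.

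Averaging the difference over the enrolled ages avoids this. With no age effect, the only cost comes from chance differences in mean age. Averaged over the DS participants' ages, the variance rises by about 1/(n − 1) = 1/49 = 2%, so the interval is about 1% wider. Averaged over both groups' ages it is about 0.5% wider. With a common slope and R² of 20% or 40%, the interval is about 10% or 22% narrower than the t-test's, for ages 3–25, 3–18 and 3–16 alike.

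**The case against.** **Age is partly handled by design.** Controls are meant to resemble the DS group, and age is the natural reading of characteristics. This stands against any claim of confounding: a reader might infer that the comparison is biased, or that the protocol ignores age altogether, and the documents support neither. It does not answer steps 1 to 3, which assume equal ages.

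**The sentence could mean a paired t-test, or a t-test on age-specific z-scores.** Both would fit the wording, but neither is stated. With individually matched controls and a common age slope, a paired t-test recovers the loss (about 69%). With a DS-only slope it gains nothing (67/64/56/46%), and it still returns one pooled mean. If matched pairs are analysed as independent, the test becomes conservative: its true level is about 2.8% at a pair correlation of 0.2.

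**The age question belongs to the longitudinal analysis.** The protocol does tie prevention and early intervention to follow-up data, and no fault is claimed in the mixed model. But that model is assigned to annual retests, not to the comparison with archive controls. The cross-sectional difference still needs an interpretable meaning over 3–25 years.

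**Such detail is commonly left to an SAP.** A separate SAP may exist, and silence alone would be no finding. Here, however, the protocol's own Statistical analysis plan paragraph names the method, and that method does not fit the Background.

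**Adjustment can do harm.** This stands for a contrast fixed at age 14 (step 5) and for a straight line imposed on an onset-then-decline pattern. Both shape the fix below.

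**Conclusion.** The point holds as a matter of analysis choice. The named test carries no age, while the protocol's own account makes age a main source of variation in DS gait and a reason to expect a changing difference from controls. Under the stated assumptions, power falls from about 69% to about 60% or 48% if a common age effect explains 20% or 40% of variance, and less if the slope is in DS only. If age explains little, almost nothing is lost.

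The power and interval figures rest on an assumed effect size, age distribution and share of variance. Bias is conditional on unequal mean ages, which the protocol neither states nor implies. Because the analysis is mainly descriptive, the consequence is modest: the change is worth considering, and the study does not fail without it.

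**What to change.** Replace the sentence on the control comparison with text such as:

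> Each gait parameter will be analysed by regression on group (DS or healthy control) and age, with a group-by-age term. The main estimate is the group difference averaged over the ages of the enrolled DS participants; differences at a few pre-stated ages within the observed range are reported descriptively. If a straight line in age does not fit, a flexible age term (for example a spline or a change in slope) or age-specific z-scores will be used. Bootstrap intervals will be used if residuals are far from normal. If controls are individually age-matched, the analysis will use the pairs.

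Under Patient Recruitment, state that age is one of the characteristics on which controls are matched, and whether matching is individual or by group. Do not fix the main contrast at age 14.

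The cost is a few sentences and some extra analysis. No new data are needed, since age is known for DS participants and is needed to select controls. The shape of the age effect must be checked. The averaged difference describes the enrolled age mix and should be reported as such: if slopes differ, its interval does not carry the nominal level for a population with another mean age. If age turns out to be irrelevant, the interval is about 0.5% to 1% wider than the t-test's, depending on whose ages are averaged over.

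### The group comparison is an age-unadjusted t-test of Dravet syndrome against healthy controls only; one age-adjusted model would also cover the planned non-SCN1A genetic control group

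*Protocol*

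**What the plan says.** The section headed Statistical analysis plan has three sentences. The first sets the scope: "The statistical analysis will mainly include descriptive statistics". The second gives the only between-group test: "Gait parameters will be compared between DS and healthy controls", by t-test or a non-parametric alternative. The third plans a mixed model for change in gait at annual retests. No sentence mentions age.

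The Patient Recruitment text sets the target ("Approximately 50 participants are being sought"), admits ages 3 to 25, and describes two sets of controls:

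- The first has typical development or cerebral palsy and comes from an existing database. It is described as "A control population in accordance with the size and characteristics of the pilot group".
- The second is definite: "a second control group will be composed of children and young adults who also have motor and developmental problems", "due to a genetic condition that is not a mutation in the SCN1A gene". No size, matching or comparison is given for it.

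The Background reports, from earlier studies, that gait declines with age in DS and that passive limitations and bony deformities increase. The Data analysis text mentions setting kinematics against age-specific reference data.

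**The concern.** The named test and the planned groups do not fit together. A test against healthy controls cannot use a control group defined by motor and developmental problems. As written, the inferential results would show that DS gait differs from healthy gait and that it changes over time. They would not show how it compares with gait in other children who have motor and developmental problems, although a group is being assembled that could answer this.

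The form of the test matters too. Age spans 22 years and is, on the protocol's own account, related to the outcome. A t-test leaves that age-related variation in the error term, so it loses some precision even against well-matched controls. If the same test were simply carried over to the genetic group, for which no matching is stated, any difference in age would be read as a difference between conditions.

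**Working it through.** **Text check: which planned groups have a stated comparison with DS?**

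| Group (Patient Recruitment) | Status | Matching to DS | Stated comparison |
|---|---|---|---|
| Typical development | planned | size and characteristics | t-test or non-parametric alternative, no age term |
| Cerebral palsy | alternative within the first population | as above | none |
| Non-SCN1A genetic condition | planned | none stated | none |

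The protocol gives no SD, effect size or power, so there is no figure of its own to reproduce. What follows is illustrative, in units of the within-group SD of a gait parameter.

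**Inputs.** From the protocol: about 50 DS participants, ages 3 to 25, and a first control population of similar size (taken as 50). Assumed: gait-age correlation ρ = 0.3 to 0.5; age SD of a uniform spread, 22/√12 = 6.35 years, used only as a scale; genetic group m = 20 or 10; mean age gap d = 3 to 5 years between DS and that group.

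**1. DS versus typical development, equal mean ages.**

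- t-test half-width: t(0.975, 98) × √(1/50 + 1/50) = 1.984 × 0.200 = 0.40 SD.
- With age in the model, the residual SD is multiplied by √(1 − ρ²). For ρ = 0.3: 1.985 × 0.954 × 0.200 = 0.38 SD. For ρ = 0.5: 1.985 × 0.866 × 0.200 = 0.34 SD.

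**2. Age gap with the genetic group if age is left out.** Shift = ρ × d / 6.35.

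| | d = 3 | d = 5 |
|---|---|---|
| ρ = 0.3 | 0.14 SD | 0.24 SD |
| ρ = 0.5 | 0.24 SD | 0.39 SD |

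**3. Precision of the age-adjusted genetic contrast.** For three groups (50, 50, m; N = 100 + m) and a common age slope, the half-width is t(0.975, N − 4) × √(1 − ρ²) × √(1/50 + 1/m + d²/((N − 3) × 6.35²)).

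- m = 20, ρ = 0.5, d = 3: 1.981 × 0.866 × √(0.0200 + 0.0500 + 0.0019) = 0.46 SD.
- m = 20, ρ = 0.3, d = 5: 1.981 × 0.954 × √(0.0200 + 0.0500 + 0.0053) = 0.52 SD.
- m = 10, same two settings: the range over all four combinations is 0.60 to 0.67 SD.
- Unadjusted, for reference: 0.53 SD (m = 20) and 0.69 SD (m = 10).

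**4. If the age slopes differ by group.** At the age midway between the two group means, the last term becomes (d/2)²/6.35² × (1/49 + 1/(m − 1)), with N − 6 degrees of freedom. For m = 20, ρ = 0.3, d = 5: 1.981 × 0.954 × √(0.0700 + 0.155 × 0.0730) = 0.54 SD. For ρ = 0.5, d = 3 it is 0.47 SD. Allowing for an interaction therefore costs little at that age, and more towards the ends of the age range.

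**The case against.** The strongest reply is that this is an omission and not an error. The section is a three-sentence summary, it says only that the analysis is mainly descriptive, and secondary contrasts and covariates are often left to a separate analysis plan. Much of this stands. Nothing rules out further analyses, so a reader should not infer that the genetic group will go unused. What remains is that the protocol does fix a method for comparing groups, and that method neither fits one of its own control groups nor uses age.

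Four stronger readings are tempting, and the document does not support them:

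- **The DS-versus-healthy comparison is biased by age.** The first control population is to resemble the patient group, and age-specific reference data are mentioned. The gain there is precision.
- **The plan has an inflated false-positive rate.** For an unadjusted t-test of 50 DS against 20 genetic controls, the shifts in step 2 would give rates of about 8% to 31%. But no such test is planned, and every input is assumed.
- **The trial sets out to test the weakness-and-malalignment hypothesis and then does not.** The Background attributes to an earlier study the idea that "a combination of malalignment and muscle weakness of the lower limbs lies at the root of the observed gait disorders", and adds that "this hypothesis can only be confirmed by 3D gait analysis in combination with measurements of muscle strength". The stated purpose, however, is to draw up treatment. No objective promises that test, and the mixed model names no covariates and so could carry strength.
- **Cerebral palsy controls are neglected in the same way.** They are worded as an alternative within the first population, so their absence from the statistical text proves little.

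**Conclusion.** The point holds as a minor one. The stated t-test is a weaker choice than the planned data allow, and it cannot cover the non-SCN1A genetic group. One age-adjusted model answers both.

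Against typical development the gain is modest: the half-width shrinks by about 5% to 13% (1 − 0.954 and 1 − 0.866). For the genetic contrast the gain is mainly in interpretation, because an age gap is no longer counted as a group difference. The sizes rest on the assumed correlation, age spread, age gap and group sizes. The mismatch between the planned groups and the stated test rests on the text alone.

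Even when adjusted, the genetic contrast would detect only fairly large differences, and it would not isolate an effect specific to DS.

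**What to change.** Keep the mixed model for annual retests. Replace the t-test sentence in the Statistical analysis plan section with wording such as:

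*Gait parameters will be compared between groups in a linear model with group, age and a group-by-age term. Planned contrasts are DS versus typically developing controls and DS versus non-SCN1A genetic controls, and DS versus cerebral palsy controls if that group is assembled. If the group-by-age term matters, differences will be reported at stated ages. A bootstrap or rank-based alternative will be used if model assumptions fail. Estimates will be given with 95% confidence intervals.*

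This gives a single analysis of DS versus typical development, so no rule of precedence is needed. The cost is a little more analysis work and wide intervals for the genetic contrast. It also assumes that the genetic group has the same gait analysis, which the protocol implies but does not state; a sentence should confirm it.

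Optional and exploratory only: relate strength and alignment to gait with age in the model, preferably within the planned mixed model, and report associations with 95% confidence intervals. The drawback is missing or non-comparable strength data, since the Data Collection Procedures text says that instructions for manual strength tests are hard for these children to follow.
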